9.1.1. Relationship to Study Drug

Adverse events will be classified as “related” to study treatment if the relationship was rated by the investigator as possibly related or probably related. Adverse events related to any study drug component (relugolix or placebo and E2/NETA or placebo) will be considered as related to study drug.

9.1.2. Severity of Adverse Event

Grade 2 or higher adverse events will be summarized by SOC, PT, and/or maximum severity, relationship to study treatment.

9.1.3. Serious Adverse Event

Serious adverse events throughout the pivotal phase 3 and extension studies will be summarized by SOC, PT, and/or maximum severity, relationship to study treatment.

The data handling conventions for and the definition of a serious adverse event are discussed in this section. All deaths during the studies, including the post treatment Follow-Up period, and deaths that resulted from a process that began during the studies, should be included in the analysis. For more details, deaths occurring during the following time periods or under the following conditions should be considered:

- Deaths occurring during participation in either the pivotal phase 3 study or extension study;
- Deaths occurring after a patient leaves the extension study, or otherwise discontinues study drug, whether or not the patient completes the study to the nominal endpoint will be included in the analysis if death is reported prior to database lock date. Death reported after that will be saved in the database but will not be analyzed.

9.1.4. Adverse Event Leading to Withdrawal of Study Drug

Adverse events leading to withdrawal of study drug are those adverse events collected from the adverse event electronic case report form (eCRF) pages with “drug withdrawn” as the action taken with study drug.

Adverse events with “drug withdrawn” as action taken due to any one of the components of study drug will be considered as leading to withdrawal of study drug.

9.1.5. Adverse Events Leading to Dose Interruption

Adverse events leading to dose interruption are those adverse events collected from the adverse event eCRF pages with “drug interrupted” as their action taken with study drug.

Adverse events with “drug interrupted” as action taken due to any one of the components of study drug will be considered as leading to dose interruption.

9.1.6. Adverse Events Resulting in a Fatal Outcome

Adverse events resulting in a fatal outcome are those adverse events collected from the adverse event pages with “fatal” as their outcome.

The fatal events, if any, will be provided in a by-subject listing.

9.1.7. Other Safety Parameters of Interest

In addition, other safety parameters of interest defined in Table 20 will be summarized by decreasing frequency of PT in the extension safety population. Additionally, event of uterine bleeding are summarized including MedDRA preferred terms: menorrhagia, metrorrhagia, menstruation irregular, vaginal haemorrhage, menometrorrhagia, polymenorrhoea, and uterine haemorrhage.

Table 20: Other Safety Parameters of Interest

Grouping	Search Criteria
Bone health related events	Osteoporosis/Osteopenia SMQ (broad) Fracture (custom SMQ): All preferred terms including the term “fracture,” excluding “Tooth fracture” and “Fracture of penis”
Hepatic transaminase elevations	Drug-related hepatic disorders – comprehensive SMQ (narrow)
Carbohydrate and lipid metabolic effects	Dyslipidemia SMQ Hyperglycemia/new onset diabetes mellitus SMQ (narrow)
Vasomotor symptoms	The following five Preferred Terms will be included: 
 • Hyperhidrosis • Feeling hot • Hot flush • Night sweats • Flushing
Mood disorders	MedDRA Depression and Suicide/Self-Injury SMQ (broad)

Abbreviations: MedDRA = Medical Dictionary for Regulatory Activities; SMQ = Standardized MedDRA Query.

9.1.8. Exposure-adjusted Adverse Events

Adverse events by time to onset and an exposure-adjusted adverse event analysis will be provided. The exposure-adjusted adverse event rate will be summarized by system organ class and preferred term for each pivotal phase 3 study treatment group, where the exposure-adjusted adverse event rate is calculated as number of patients with a particular adverse event by total exposure-time among patients at risk of an initial occurrence of the event. Exposure-time is derived as exposure to any study drug throughout the pivotal phase 3 studies and extension study.

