4.3.5. Definition of Overall Treatment Duration

In the final analysis, overall treatment duration is defined as the duration of time from the date of the first dose of pivotal phase 3 study drug to the date of the last dose of extension study drug as follows:

$$(\text{Date of last dose of extension study drug} - \text{Date of first dose of pivotal phase 3 study drug}) + 1$$

For patients missing day and month of the last dose date of extension study drug, the last date extension study drug was dispensed will be used to calculate overall treatment duration. For patients missing only day for date of last dose of extension study drug, the later of first of the month of last dose of extension drug or last date extension study drug was dispensed will be used to calculate treatment duration.

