9.1. Adverse Events

Adverse events will be collected from the time of the first dose of open-label study drug through the safety Follow up visit approximately 30 days after the last dose of open-label study drug (the end of extension treatment period), or the date of initiation of another investigational agent or hormonal therapy or surgical intervention affecting the hypothalamic-pituitary-gonadal axis or surgical intervention for endometriosis, whichever occurs first, as also specified in the Schedule of Activities in the study protocol Section 1.1. Additionally, serious adverse events reported to the investigator after the safety reporting period should be reported to the sponsor regardless of causal relationship to study drug treatment.

Using a Safety Report Form, all serious adverse events must be reported within 24 hours of the study site personnel's knowledge of the event, regardless of the investigator assessment of the relationship of the event to study drug.

The severity of all treatment-emergent adverse events will be evaluated by the investigator based on the National Cancer Institute's Common Terminology Criteria for Adverse Events (CTCAE, version 5.0 dated 27 Nov 2017), and will be coded to preferred term and system organ class using MedDRA 22.0 or higher.

A treatment-emergent adverse event is defined as any adverse event that occurs after administration of the first dose of pivotal phase 3 study drug.

Adverse event summaries will be based on treatment-emergent adverse events in the pivotal phase 3 and extension studies, unless otherwise specified. All adverse events in the pivotal phase 3 and extension studies will be listed in by-patient listings.

The following tabular summaries that include the number and percentage of patients will be provided:

- Overview of adverse events;
 - Safety parameters of interest

- Safety parameters of interest with first onset during extension study
- All adverse events;
 - By SOC and PT;
 - By decreasing frequency of PT;
 - By SOC, PT, and maximum severity;
 - Study drug-related per investigator by SOC and PT;
 - By time to onset (Day 1 to Week 24, > Week 24 to Week 52, >Week 52 to Week 78, > Week 78 to Week 104, > Week 104), SOC and PT;
 - Exposure-adjusted AE rate by SOC and PT
- Adverse events reported in at least 5% of patients in any treatment group
 - By decreasing frequency of PT;
- Grade 3 or above adverse events;
 - By SOC and PT;
 - By decreasing frequency of PT;

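### Section 9.1.8: the exposure-adjusted adverse event rate counts events into the off-drug follow-up but divides by exposure that ends at the last dose

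*SAP*

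**What the plan says.** Section 9.1.8 defines the rate, by pivotal treatment group, as "number of patients with a particular adverse event by total exposure-time among patients at risk of an initial occurrence of the event". It then fixes the person-time: "Exposure-time is derived as exposure to any study drug throughout the pivotal phase 3 studies and extension study". Section 6 makes clear that any study drug includes placebo. Section 4.3.5 runs overall treatment duration from "the date of the first dose of pivotal phase 3 study drug to the date of the last dose of extension study drug", and Section 4.3.6 ends extension treatment duration at the same point.

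The events come from Section 9.1. Collection continues "through the safety Follow up visit approximately 30 days after the last dose of open-label study drug", or stops sooner if another investigational agent, hormonal therapy or relevant surgery begins. The definition of treatment-emergent has a start but no end: "A treatment-emergent adverse event is defined as any adverse event that occurs after administration of the first dose of pivotal phase 3 study drug". The default event set is broad: "Adverse event summaries will be based on treatment-emergent adverse events in the pivotal phase 3 and extension studies, unless otherwise specified". The exposure-adjusted rate is one of the summaries listed under that default, and Section 9.1.8 sets no on-drug limit. Section 4.2 also takes safety data in the final analysis up to the safety Follow-Up.

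**The concern.** A rate needs events and time at risk from the same period. Here, a first event 20 days after the last dose counts in the numerator, while none of those 20 days counts in the denominator. No section adds follow-up days to exposure-time or removes follow-up events from the count.

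A programmer cannot be expected to assume an on-drug cut-off. Where the SAP wants one it says so: several Section 9.1 tables are restricted to events resolved before the last dose date. Section 4.4.2 refers to an end date of the treatment-emergent period, but none is defined. At stake is what the tabulated rate means and how it may be labelled. No formal test depends on it.

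**Working it through.** The SAP gives no adverse event rate or early-stopping figure, so there is nothing to reproduce. Hazards and stopping patterns below are assumptions.

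**Inputs**
- Completer exposure: 24 + 80 = 104 weeks = 728 days (Section 5.1).
- Shortest plausible exposure: about 168 days, because entrants completed a 24-week pivotal study (Section 2.1).
- Off-drug collection: about 30 days (Section 9.1).

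**1. Ceiling at constant hazard.** For a rare event, the SAP rate divided by a rate with matched person-time is (E + 30)/E, where E is days of exposure.

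| Weeks on drug | E (days) | (E + 30)/E | Overstatement |
|---|---|---|---|
| 104 | 728 | 758/728 | 4.1% |
| 78 | 546 | 576/546 | 5.5% |
| 52 | 364 | 394/364 | 8.2% |
| 28 | 196 | 226/196 | 15.3% |
| 24 | 168 | 198/168 | 17.9% |

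**2. Group level.** The rate is shown by pivotal group, not by duration. Suppose a share d stops early, uniformly between Weeks 24 and 104. Mean exposure is (1 − d) × 728 + d × 448 days, since (168 + 728)/2 = 448.
- d = 0: 758/728 = 1.041.
- d = 0.5: mean 588 days, 618/588 = 1.051.

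The overstatement is 4.1% to 5.1%. Between a group with no early stopping and one with half stopping early, the difference is about 1 percentage point.

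**3. Common events.** A woman who already had the event is no longer at risk in follow-up. With person-time cut at the first event, the ratio is (1 − exp(−h(E + 30)))/(1 − exp(−hE)), with time in years. For E = 728 days:
- h = 20 per 100 patient-years: 0.3397/0.3288 = 1.033.
- h = 50 per 100 patient-years: 0.6457/0.6309 = 1.024.

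With step 2, this gives about 2% to 5% at group level.

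**4. Events concentrated after stopping.** Assume 1 per 100 patient-years on drug and 100 per 100 in the 30 days after.
- 728 days on drug: SAP rate 4.92, matched rate 4.73, on-drug rate 1.00.
- 196 days on drug: SAP rate 15.66, matched rate 13.65, on-drug rate 1.00.

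Against a matched rate the excess stays near 30/E (4% and 15%). The large gap appears only if the figure is read as an on-drug rate.

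**5. If person-time is not cut at the first event.** Take 20 per 100 patient-years on and off drug and E = 728 days (1.993 years). The proportion with an event by day 758 is 0.3397, and 0.3397/1.993 = 17.0 per 100 patient-years instead of 20.0. The net error then runs downward.

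**The case against.** The strongest objection is that the effect is small where the rate is displayed: a few per cent in one descriptive table, with no formal comparisons planned (Sections 4.1 and 7.1). Events are also shown by time to onset and listed by patient. This stands as to size. It does not make the two periods agree.

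Section 9.1 appears to call the follow-up visit the end of the extension treatment period, so exposure might be thought to reach that far. But Sections 4.3.5 and 4.3.6 stop at the last dose, and Section 9.1.8 speaks of exposure to drug. At most this leaves two readings of the denominator.

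The last onset band, "> Week 78 to Week 104, > Week 104), SOC and PT", is weak evidence of off-drug counting. Section 2.1 allows the first extension dose up to 10 days after the Week 24 visit, so some onsets beyond Week 104 can be on drug. The point does not need this band.

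Three stronger readings are tempting, and the SAP does not support them:
- **Rates per year of relugolix.** The denominator is any study drug, including placebo time in the pivotal studies.
- **A materially distorted display across pivotal groups.** Even very different early stopping moves the groups apart by about 1 percentage point, and the SAP gives no stopping figures.
- **Inflation by returning bleeding or pain.** Menstruation recovery has its own table (Section 9.3.6) and pain is recorded in the eDiary. The SAP does not say that either, when expected after stopping, is reported as an adverse event.

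**Conclusion.** The mismatch is real as written: events run to the safety Follow-Up, while exposure ends at the last dose. If person-time is cut at the first event, constant-hazard rates are overstated by at most 30/E. That is about 2% to 5% at group level, at most 4.1% for a 728-day completer, and up to about 18% in the contribution of a woman stopping just after Week 24. A larger departure from an on-drug rate arises only for events concentrated after stopping.

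These sizes rest on 30 days of follow-up, a constant hazard, and 0% to 50% stopping early at uniformly spread times. Follow-up can be shorter if another therapy starts. If events were counted to 60 days, the upper end of the Safety Follow-Up visit window in Table 3, the group-level range for rare events would be 8.2% to 10.2%.

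A reader might infer that every rate is overstated. That does not follow. The phrase about patients at risk of an initial occurrence suggests a cut at the first event, but the next sentence can be read as full exposure. Under the second reading, rates for common events are understated. This is a modest, inexpensive correction to a descriptive analysis.

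**What to change.** Amend Section 9.1.8 so that both parts use one risk period, by either route:
- **On-treatment rate:** count only first onsets up to the last dose, over exposure time.
- **On-study rate:** keep follow-up events and add each woman's follow-up days to the person-time. Run these to the earliest of the safety Follow-Up visit, the start of another investigational agent, hormonal therapy or surgical intervention, or last contact. Label the rate as on-study.

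In the same edit, state that person-time is cut at a woman's first event of the type being counted, and give the end date of the treatment-emergent period to which Section 4.4.2 refers. The cost is a few sentences and a small programming change, with no new data collection.

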9.1.9. Adverse Events of Clinical Interest

Adverse Events of clinical interest in the pivotal phase 3 studies and the extension study are defined as any increase in ALT or AST $\geq 3 \times$ ULN, which are reported as “Yes” for adverse events of clinical interest in the adverse event CRF. Adverse events of clinical interest will be summarized by PT.

9.2. Laboratory Data

Laboratory parameters, including chemistry and hematology panels, and hormonal tests specified as per protocol for the pivotal phase 3 and extension studies, and collected from the central laboratory will be tabulated and presented in by-patient listings. Except for the tables using pre-defined threshold for chemistry and hematology parameters, local laboratory parameters will not be presented in tables. The local laboratory parameters will be presented in by-patient listings. Urinalysis and hepatitis virus serological test results will be provided in by-patient listing only.

For patients with incomplete recovery of bone mineral density loss at the 6- and 12-month post-treatment Follow-Up visit, clinical laboratory tests specified in the protocol should be performed. These laboratory assessments will be submitted to the central laboratory. If these laboratory assessments are scheduled to occur after the study database is locked, they will be performed at a local laboratory.

The National Cancer Institute CTCAE Grading Scale with numeric component will be used to categorize toxicity grade for laboratory parameters (CTCAE v5.0, dated 27 Nov 2017). Parameters that have criteria available for both low and high values (eg, hypercalcemia for a high value of calcium and hypocalcemia for a low value of calcium) will be summarized for both criteria (low and high). Patients will only be counted once for each criterion. The same patient can be counted for both criteria (ie, low and high) if she has laboratory values meeting each criterion. Shift tables will be provided for each parameter gradable by the CTCAE to summarize Baseline toxicity grade versus worst post-Baseline toxicity grade throughout the pivotal phase 3 and extension studies. For laboratory parameters that are not gradable by the CTCAE, a shift table based upon the normal range (low, normal, and high) will be provided for each parameter to summarize the Baseline versus worst post-Baseline results throughout the pivotal phase 3 and extension studies. A shift table for selected parameters based on predefined categories will be provided to summarize baseline category versus post-baseline category at Week 104. The parameters include glucose (< 100 mg/dL, 100 - 125 mg/dL, 126 - 200 mg/dl, > 200 mg/dL), fasting glucose (< 100 mg/dL, 100 - 125 mg/dL, 126 - 200 mg/dl, > 200 mg/dL), HbA1c (<= 5.6%, 5.7% - 6.4%, 6.5% - 8.0%, 8.1% - 9.4%, 9.5% - 11%, > 11%), low density cholesterol (normal <100 mg/dL, normal high 100 to < 130 mg/dL, borderline high 130 to < 160 mg/dL, high 160 to < 190 mg/dL, very high >= 190 mg/dL), high density cholesterol (< 40 mg/dL, 40 - 59 mg/dL, >= 60 mg/dL), triglycerides (< 150 mg/dL, 150 - 300 mg/dL, 301 - 500 mg/dL, 501 - 1000 mg/dL, > 1000 mg/dL) and total cholesterol (<= ULN, > ULN - 300 mg/dL, > 300 - 400 mg/dL, > 400 - 500 mg/dL, > 500 mg/dL).

Boxplots of laboratory values over time, including visits in both the pivotal phase 3 study and extension study, will be plotted for key laboratory parameters. These laboratory parameters include, but are not limited to, hematology (hemoglobin, platelets, leukocytes, neutrophils), creatinine, estimated glomerular filtration rate, and hepatic function panel (alanine aminotransferase [ALT], aspartate aminotransferase [AST], alkaline phosphatase [ALP], and total bilirubin).

The change from Baseline to each post-Baseline study visit will be presented by pivotal phase 3 study treatment group for each laboratory test in both tables and figures.

The number and proportion of patients with liver test elevations will be presented by pivotal phase 3 study treatment group. Liver test elevations are assessed by using post-Baseline results for ALT, AST, ALP, and total bilirubin based on the definitions presented in Table 21. The number and percentage of patients with concurrent (defined as measurements on the same day) ALT or AST $\geq 3 \times$ ULN and total bilirubin $> 2 \times$ ULN, Concurrent ALT or AST $\geq 3 \times$ ULN and total bilirubin $> 2 \times$ ULN and ALP $< 2 \times$ ULN will also be presented. A by-patient listing will also be provided,

Table 21: Categories of Liver Test Elevations

Laboratory Test	Category
ALT or AST	ALT or AST > ULN < 3 × ULN ALT or AST ≥ 3 × to < 5 × ULN ALT or AST ≥ 5 × to < 10 × ULN ALT or AST ≥ 10 to < 20 × ULN ALT or AST ≥ 20 × ULN
Total bilirubin	Total bilirubin > 2 × ULN
ALT or AST and total bilirubin	Concurrent ALT or AST ≥ 3 × ULN and total bilirubin > 2 × ULN
ALT or AST, total bilirubin, and ALP	Concurrent ALT or AST ≥ 3 × ULN and total bilirubin > 2 × ULN and ALP < 2 × ULN

Abbreviations: ALP = alkaline phosphatase; ALT = alanine aminotransferase; AST = aspartate aminotransferase; ULN = upper limit of normal.

Selected chemistry and hematology test results meeting pre-defined limits of change at any time and based on last observation on treatment will be also summarized per pre-defined threshold (refer to [Appendix 2](#)) **Error! Reference source not found.** by pivotal phase 3 study treatment group.

9.3. Other Safety Analyses

9.3.1. Electrocardiograms

ECG interval results and changes from Baseline will be summarized descriptively for each scheduled visit, including visits in both the pivotal phase 3 studies and extension study, in both tables and figures using data provided by and read by central reading.

A categorical analysis of corrected QT interval using Fridericia's calculation (QTcF) intervals will also be performed for each scheduled visit and for the maximum post-Baseline value. The number and percentage of patients in each QTcF interval category (< 450 msec, 450 to 480 msec, 481 to 500 msec, and > 500 msec) will be summarized. Categories of changes from Baseline (≥ 30 msec and ≥ 60 msec) will be summarized as well.

ECG intervals and central reader interpretation and diagnoses will be presented in by-patient listings.

9.3.2. Vital Signs

Blood pressure (systolic and diastolic), heart rate, and BMI will be summarized at pivotal phase 3 study Baseline and each subsequent scheduled assessment, including visits in both the pivotal phase 3 study and extension study, by pivotal phase 3 study treatment group. Change from pivotal phase 3 study Baseline will be calculated and presented for each parameter at all scheduled post-Baseline assessment time points in both tables and figures. All vital sign data will also be provided in by-patient listings.

Potentially clinically significant abnormalities in vital signs are defined in Table 22, and they will be summarized by using post-Baseline values that meet the defined criteria. Potentially clinically significant abnormalities will also be flagged in by-patient listings.

Table 22: Categories of Potentially Clinically Significant Abnormalities in Vital Signs

Parameter	Category
Systolic blood pressure	≥ 140 mmHg over 2 consecutive visits ≥ 180 mmHg over 2 consecutive visits ≤ 90 mmHg over 2 consecutive visits
	≥ 140 mmHg and $>$ highest screening or baseline in pivotal phase 3 studies over 2 consecutive visits; ≥ 180 mmHg and $>$ highest screening or baseline in pivotal phase 3 studies over 2 consecutive visits
	≤ 90 mmHg and $<$ lowest screening or baseline in pivotal phase 3 studies over 2 consecutive visits
	Increase of ≥ 20 mmHg from Baseline in pivotal phase 3 studies over 2 consecutive visits Decrease of ≥ 20 mmHg from Baseline in pivotal phase 3 studies over 2 consecutive visits
Diastolic blood pressure	≥ 90 mmHg over 2 consecutive visits ≥ 105 mmHg over 2 consecutive visits ≤ 50 mmHg over 2 consecutive visits
	≥ 90 mmHg and $>$ highest screening or baseline in pivotal phase 3 studies over 2 consecutive visits ≥ 105 mmHg and $>$ highest screening or baseline in pivotal phase 3 studies over 2 consecutive visits
	≤ 50 mmHg and $<$ lowest screening or baseline in pivotal phase 3 studies over 2 consecutive visits
	Increase of ≥ 15 mmHg from Baseline in pivotal phase 3 studies over 2 consecutive visits Decrease of ≥ 15 mmHg from Baseline in pivotal phase 3 studies over 2 consecutive visits
Heart rate	≥ 120 bpm and $>$ highest screening or baseline in pivotal phase 3 studies over 2 consecutive visits
	< 45 bpm and $<$ lowest screening or baseline in pivotal phase 3 studies over 2 consecutive visits
	Increase of ≥ 15 bpm from Baseline in pivotal phase 3 studies over 2 consecutive visits Decrease of ≥ 15 bpm from Baseline in pivotal phase 3 studies over 2 consecutive visits

Abbreviations: bpm = beats per minute; mmHg = millimeters of mercury.

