4. GENERAL CONSIDERATIONS FOR DATA ANALYSES AND HANDLING OF MISSING DATA

4.1. Data Presentation Conventions

All statistical analyses will be conducted using SAS[®] Version 9.2 or higher. Only descriptive analyses will be provided. Formal statistical comparisons are not planned.

All confidence intervals (Cis) will be reported as two-sided 95% Cis unless otherwise stated.

Where appropriate, variables will be summarized descriptively by study visit. For the categorical variables, the count and proportions of each possible value will be tabulated by pivotal phase 3 study treatment group. For continuous variables, the number of patients with non-missing values, mean, median, standard deviation (SD), minimum, and maximum values will be tabulated.

Unless otherwise specified, the following conventions will be applied to all analyses:

- Mean and median values will be formatted to one decimal place, unless otherwise specified. For BMD DXA, mean and median values will be formatted to two decimal places. Standard deviation values will be formatted to two more decimal places, unless otherwise specified. Minimum and maximum values will be presented to the same number of decimal places as the measured value. If the measured value is large (eg, > 100), fewer decimal places may be displayed.
- Percentages will be rounded to one decimal place.
- P values will be rounded to four decimal places. P values < 0.0001 will be presented as "< 0.0001" and p values > 0.9999 will be presented as "> 0.9999".
- 1 month = 30.4375 days. Month is calculated as (days/30.4375) rounded to one decimal place.
- 1 year = 365.25 days. Year is calculated as (days/365.25) rounded to one decimal place.
- Age will be calculated using the date of randomization in pivotal phase 3 study. If only year of birth is collected, 1 July of the year of birth will be used to calculate age.
- 1 pound = 0.454 kg.
- 1 inch = 2.54 cm.
- Missing efficacy or safety data will not be imputed, unless otherwise specified.
- For laboratory results above or below sensitivity limits displayed as "<" or ">" a quantification threshold, 0.000000001 will be subtracted or added, respectively, to the threshold to derive a numeric result for analysis.
- For safety analyses, percentages will be calculated based on the number of patients in the analysis population in each pivotal phase 3 study treatment group.

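### Table 22 counts SBP ≥ 180, DBP ≥ 105 and heart rate ≥ 120 or < 45 only when they persist over two successive visits, so isolated extreme readings are neither counted nor flagged in those categories

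*SAP*

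**What the plan says.** SAP Section 9.3.2 (Vital Signs) uses Table 22 both to decide which post-Baseline values are summarised as potentially clinically significant and to mark the listings: "Potentially clinically significant abnormalities will also be flagged in by-patient listings". There is no other definition.

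The highest systolic category is "≥ 180 mmHg over 2 consecutive visits" and the highest diastolic category is "≥ 105 mmHg over 2 consecutive visits". Each has a second version that also requires the value to exceed the highest screening or baseline value. Heart rate has one high and one low absolute category: "≥ 120 bpm and $>$ highest screening or baseline in pivotal phase 3 studies over 2 consecutive visits" and "< 45 bpm and $<$ lowest screening or baseline in pivotal phase 3 studies over 2 consecutive visits". The change-from-Baseline rows follow the same pattern, for example "Increase of ≥ 15 bpm from Baseline in pivotal phase 3 studies over 2 consecutive visits".

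Section 9.3.2 also provides a listing of all vital sign data and summaries at each scheduled assessment. Under Section 4.1 the summaries of continuous variables report "mean, median, standard deviation (SD), minimum, and maximum values will be tabulated".

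**The concern.** Requiring two successive visits is a reasonable noise filter at mild thresholds such as 140/90 mmHg. As the only rule at 180/105 mmHg, or at heart rate 120 and 45 bpm, it removes readings a safety reviewer would want counted. These include an extreme value that was treated and came down, one followed by withdrawal from the study, and one first seen at the last visit. In each case there may be no second qualifying reading.

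Long-term safety is a stated objective of the study. A table presented as the summary of potentially clinically significant vital signs would then describe sustained abnormalities only. A reader could take a zero in the ≥ 180 row to mean that no woman reached that value.

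**Working it through.** The plan gives no expected count or rate for this point, so there is no figure to reproduce. The check is to read every row and apply the rule.

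**Row count (Table 22).** Systolic 8 + diastolic 8 + heart rate 4 = 20 rows, and all 20 require two consecutive visits. The extreme rows are SBP ≥ 180 (2), DBP ≥ 105 (2), heart rate ≥ 120 (1) and heart rate < 45 (1), so 2 + 2 + 1 + 1 = 6. No row uses a single reading or a worst post-Baseline value.

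**Rule applied to constructed series.** A row is met if two adjacent readings both satisfy it. The series and reference values are assumptions chosen to show the logic:

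- SBP: baseline 125, highest/lowest screening or baseline value 130/120, so an increase ≥ 20 means ≥ 145.
- DBP: baseline 80, highest/lowest 84/76, so an increase ≥ 15 means ≥ 95.
- Heart rate: baseline 75, highest/lowest 82/68, so an increase ≥ 15 means ≥ 90 and a decrease ≥ 15 means ≤ 60.

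| Series at successive visits | Table 22 rows met | In its extreme row? |
|---|---|---|
| SBP 128, 185, 130, 126 | none | no |
| SBP 126, 128, 130, 185 | none | no |
| SBP 128, 185, 150, 130 | ≥ 140 (both versions), increase ≥ 20 | no |
| SBP 128, 182, 181, 130 | ≥ 140 and ≥ 180 (both versions of each), increase ≥ 20 | yes |
| DBP 80, 108, 82, 80 | none | no |
| DBP 80, 108, 95, 82 | ≥ 90 (both versions), increase ≥ 15 | no |
| HR 74, 125, 78, 76 | none | no |
| HR 74, 125, 100, 76 | increase ≥ 15 | no |
| HR 74, 42, 70, 72 | none | no |

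The existing extreme rows count 1 of 9; an any-time row would count 9 of 9. Three systolic readings of 200 at non-adjacent visits, with 130 at all others, also meet neither ≥ 140 nor ≥ 180.

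**Visit spacing.** Table 3 target days are 28 days apart up to Week 52 and then 365, 456, 547, 638 and 731, giving gaps of 91, 91, 91 and 93 days. If vital signs are taken at these visits and only scheduled readings qualify, a woman in the second year must hold SBP ≥ 180 at two visits about three months apart to be counted.

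**Comparison within the SAP.** Section 9.3.1 says the QTcF categories "will also be performed for each scheduled visit and for the maximum post-Baseline value". Section 9.2 counts selected laboratory limits met at any point, as well as at the last on-treatment observation. Neither requires persistence.

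**Sensitivity, on assumed inputs only.** Take 17 visits, a per-visit probability p of an extreme reading, and a probability q that an extreme reading is followed by another at the next visit. The chance of moving from non-extreme to extreme is then r = p(1 − q)/(1 − p). For p from 0.1% to 1%, the share of women with any extreme reading whom the two-visit rule captures is 9.5–10.0% at q = 10%, 28.4–29.3% at q = 30% and 47.3–48.2% at q = 50%. The share stays close to q and barely depends on p. Nothing in the SAP informs p or q, so this shows how the rule behaves and does not estimate the undercount.

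**The case against.** The strongest reply is that Table 22 openly and uniformly defines sustained abnormality and never claims to count any-time extremes. Clinic blood pressure and heart rate differ from centrally read ECGs and central laboratory results, so a persistence rule for them contradicts nothing. The readings are not lost either: all are listed, a by-visit maximum or minimum can reveal them, and a woman who was treated or withdrawn may well appear in the adverse event tables. The SAP also leaves a consecutive visit undefined. If an unscheduled recheck or a Safety Follow-Up reading counts, some of the cases described above would qualify. Finally, the study is single-arm and descriptive, its listed safety endpoints are adverse events and bone mineral density, and 120 and 45 bpm are simply the only absolute heart-rate thresholds, not an upper tier.

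Much of this stands. It limits the severity, and it means the practical loss depends partly on an unstated definition. It does not close the gap. A by-visit maximum gives one value per visit and group, an unflagged listing must be searched by hand, and adverse event reporting depends on the investigator's judgement. None gives the number of women who crossed the threshold. Counting rechecks as visits would help only where the recheck was itself extreme.

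**Conclusion.** The point holds. As written, Table 22 and its listing flag omit any isolated reading from the SBP ≥ 180, DBP ≥ 105, heart rate ≥ 120 and heart rate < 45 categories. Such a woman may still appear in a milder row if an adjacent reading meets that row's condition.

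The size of the undercount cannot be derived from the SAP. The conclusion rests on the table's wording alone and needs no assumption about frequency. How often it matters depends on how common and how persistent such readings are, and on what counts as a consecutive visit. The primary analysis and all other estimates are unaffected. This is a worthwhile improvement to descriptive safety reporting that the sponsor should consider.

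**What to change.** Keep all 20 rows as the summary of sustained abnormalities, which leaves them unchanged for any comparison with the pivotal studies. Add four rows for any post-Baseline assessment, including unscheduled and Early Termination readings:

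- SBP ≥ 180 mmHg
- DBP ≥ 105 mmHg
- heart rate ≥ 120 bpm and above the highest screening or baseline value
- heart rate < 45 bpm and below the lowest screening or baseline value

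Flag the same readings in the by-patient listing. In Section 9.3.2, also state which readings form a pair of consecutive visits: scheduled only, or scheduled plus unscheduled, Early Termination and Safety Follow-Up.

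The cost is SAP wording, four table rows and one listing flag on data already collected. The drawback is that some isolated and possibly spurious readings will be counted. The sustained rows alongside give the context to judge them.
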